#### 1.4.8 Primary endpoint

This study is exploratory and therefore, there is no primary endpoint.

#### 1.4.9 Statistical hypotheses and sample size

This is an exploratory study; therefore, the sample size is not only based on statistical considerations, but also on practical considerations such as the amount of subjects available and willing to participate in the Netherlands. Motivation to participate in clinical studies in the population is high, but the absolute numbers are limited (around 60 patients in the Netherlands). We expect to be able to recruit 20 subjects within a feasible timeline.

Still, we are able to calculate the power of the chosen exploratory endpoints and sample size. The CGI-I has a standard deviation of 1.5 points. This study has an 80% power to detect a 1 point difference in CGI-I. Assuming a sample size of 20 subjects and a drop-out rate of 20%, we can detect the following effect sizes for NeuroCart tests:

Test	Minimum detectable effect size (MDES)	Corresponding proportion of the difference between ARID1B and control subjects
Animal fluency test	3.3 animals	24%
Finger tapping	2.2 taps	21%
Adaptive tracking	1.35%	8%
Smooth pursuit eye movement	5.32%	25%
Saccadic eye movements		
- Peak velocity	13.95 degrees/s	NA
- Reaction time	0.0286 sec	NA
Body sway	301 mm	37%

## 2 STUDY OBJECTIVES

- To test the hypothesis that clonazepam administration has acute beneficial effects compared to placebo on neurocognitive tests.
- To test the hypothesis that multiple-doses clonazepam has beneficial effects compared to placebo on behaviour and cognitive function in ARID1B patients as measured by the ABC, and CGI-I scale.
- Assess safety and tolerability of clonazepam in ARID1B patients.
- To assess the potential of at-home neurocognitive tests for the evaluation of treatment effects in children with neurodevelopmental disorders.
- To assess and compare the difference in predictive capability between linear and nonlinear (NONMEM) regression of the saliva:plasma relationship.

## 3 STUDY DESIGN

## 3.1 Overall study design and plan

**Part A.** Open label study in healthy volunteers where pharmacokinetics of clonazepam will be measured in paired plasma and saliva samples. Detailed scheduling can be found in **Table 1**.

For part A, the total duration of the study for each subject will be up to 2 days divided as follows:

- Screening: Up to 28 days before dosing.
- Saliva PK study day: Day 1.

**Part B.** Two-way cross over, placebo-controlled randomized study. Each period will be 22 days and periods will be separated by approximately a three-week washout. Patients will be monitored in the clinic for 5 hours for safety, PK, and biomarker effects on day 1 and 22 in each period. Within those days, patients remain at home and fill in questionnaires, wear a smartwatch and perform home-based assessments. Detailed scheduling can be found in **Table 2**.

For part B, the total duration of the study for each subject is divided as follows:

- Screening: By telephone, up to 60 days before dosing;
- In clinic study days study period 1: Day 1 22 plus a down titration period of ±3 days;
- In clinic study days study period 2: Day 1 22 plus a down titration period of ±3 days;
- Trial@Home periods: Days 2-21
- Follow-up phone call: approximately 14 days after the last dose of each study period.

## 4 STUDY POPULATION

## 4.1 Subject population

For part A, subjects will be recruited via media advertisement or from the subjects' database of the Centre for Human Drug Research, Leiden, the Netherlands. For part B, ARID1B-related ID patients will be recruited via the LUMC's expertise centre for Coffin-Siris syndrome. If required, additional patients will be identified through the 8 clinical genetic laboratories who may have diagnosed ARID1B patients.

## 4.2 Inclusion criteria

Part A, healthy volunteers.

- 1. Healthy male or female volunteers aged 18-30 years
- 2. Informed consent provided by volunteer

Part B, ARID1B patients.

- 1. Informed consent provided by both parents, or the legal guardian prior to any study mandated procedure.
- 2. Known mutation in ARID1B
- 3. Assent provided by the participant.
- 4. Aged 6 years or older

## 4.3 Exclusion criteria

Part A, healthy volunteers

- 1. Disorder that could interfere with saliva production.
- 2. Known hypersensitivity to clonazepam, other benzodiazepines or other excipients of the study medication.
- 3. Treatment with another investigational drug within 3 months prior to screening or more than 4 times a year.
- 4. History or clinical evidence of any disease and/or existence of a surgical or medical condition which might interfere with the absorption, distribution, metabolism or excretion of the study drug.
- 5. History of severe respiratory problems or severe liver- or renal insufficiency.
- 6. Other medical or psychosocial condition or history making the participant unsuitable for participation.
- 7. History or clinical evidence of alcoholism within the 3-year period prior to screening (i.e. regular use of more than 21 units of alcohol/week).
- 8. Clinically significant findings on physical examination.
- 9. Medications with a strong influence on CYP3A4 metabolism
- 10. Clinically meaningful blood loss (including blood donation), or a transfusion of any blood product within 12 weeks before screening.

Part B, ARID1B patients.

- 1. Clear indication of not wanting to participate during the study
- 2. Use of benzodiazepines or any other medication or drug with the potential to influence study related endpoints in the investigator's opinion (including e.g. CYP3A4-related drugs).
- 3. Known hypersensitivity to clonazepam, other benzodiazepines or other excipients of the study medication.
- 4. History of severe respiratory problems or severe liver- or renal insufficiency.

5. Other medical or psychosocial history making the participant unsuitable for participation as determined by the treating physician or general practitioner.

## 4.4 Concomitant medications

All prescription medications taken within 30 days of study screening will be recorded. Medication known to influence CNS-activity will be assessed for each patient. Subjects will be allowed to participate when they have been on a stable dose for at least 3 months prior to the first study day. Medications with a strong influence on CYP3A4 metabolism are an exclusion criterion.

## 4.5 Lifestyle restrictions

Alcohol will not be allowed from at least 24 hours before each scheduled visit, and whilst in the study unit. At other times throughout the study, subjects should not consume more than 2 units of alcohol daily on average (one unit is 10 grams of alcohol).

Subjects will not be allowed to have excessive caffeine consumption, defined as >800 mg per day from 7 days prior to the first study day. Subjects will abstain from caffeine-containing products for 24 hours prior to the start of the study. Caffeine quantities defined as: one cup of coffee contains 100 mg of caffeine; one cup of tea, or one glass of cola, or potion of chocolate (dark:100 g, milk 200 g) contains approximately 40 mg of caffeine; one bottle of Red Bull contains approximately 80 mg of caffeine.

Any nutrients known to modulate CYP enzymes activity (e.g., grapefruit or Seville orange containing products or quinine containing drinks (tonic water or bitter lemon)) will not be permitted from 3 days before dosing until 24 hours after the final dose.

The use of (illicit) drugs including cannabis can influence the measurements. Therefore, using 'drugs' is not permitted from 3 days before dosing and until the end of the study. Subjects will abstain from the use of tobacco-or nicotine-containing products (including e-cigarettes and patches) for 24 hours prior to dosing until the end of the study.

Strenuous physical activity (e.g., heavy lifting, weight or fitness training) is not allowed from 48 hours prior to each study day until collection of the final pharmacokinetic blood sample discharge from the study unit. Light ambulatory activities (e.g. walking at normal pace) will be permitted, with the level of activities kept as similar as possible on all days in the study unit.

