## Part B:

The following substances will be administered:

- Active medication. Clonazepam (Rivotril) droplets for oral use, solution 2.5 mg/ml, dissolved in lemonade, tea or juice.
- Placebo: dissolved in lemonade, tea or juice

Study drug or placebo during part B will be administered to the subjects as follows:

- Day 1-3: Starting dose is 0.005 mg/kg, twice daily (max 0.5 mg, twice daily)
- Day 4-6: 0.01 mg/kg, twice daily (max 0.5 mg, twice daily)
- Day 7-22: 0.015 mg/kg, twice daily (max 0.5 mg, twice daily)

Patients will receive a single starting dose at their first visit of 0.005 mg/kg (max 0.5 mg). Patients will be monitored for 5 hours for safety, PK, and biomarker effect. If the dose on day 1 is well tolerated, patients will take the same dose before bedtime, and continue this regimen as described.

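### The 24-hour caffeine abstinence covers only the start of the study, and Part B doses may be given in tea, so caffeine is only loosely controlled on the NeuroCart days

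*Protocol*

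**What the plan says.** Protocol section 4.5 (Lifestyle restrictions) contains two caffeine rules. The first is a cap: "Subjects will not be allowed to have excessive caffeine consumption, defined as >800 mg per day from 7 days prior to the first study day". No end date is given. The second is full abstinence: "Subjects will abstain from caffeine-containing products for 24 hours prior to the start of the study". The section then defines caffeine quantities. It assigns 100 mg to a cup of coffee, and adds that "one cup of tea, or one glass of cola, or potion of chocolate (dark:100 g, milk 200 g) contains approximately 40 mg of caffeine".

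The alcohol rule in the same section is worded differently: "Alcohol will not be allowed from at least 24 hours before each scheduled visit, and whilst in the study unit". The exercise restriction is likewise tied to each study day.

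For Part B, section 5.1 and the synopsis describe the active product as "Clonazepam (Rivotril) droplets for oral use, solution 2.5 mg/ml, dissolved in lemonade, tea or juice", and the comparator as "Placebo: dissolved in lemonade, tea or juice". For Part A, which has no cognitive testing, only lemonade is named.

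Section 3.1 has patients in the clinic for "biomarker effects on day 1 and 22 in each period". Table 2 places the dose at 0 h and the NeuroCart battery at -1, 1, 3 and 5 h on each of those days.

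**The concern.** The abstinence rule is anchored to a single moment, while the measurements it would protect are repeated on four days. The wording suits a study with one dosing day, such as Part A. It does not suit a crossover with two clinic days in each of two periods.

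The tea option adds a second gap. The protocol treats tea as a caffeine source in one section and permits it as the dosing vehicle in another, shortly before three of the day's four batteries.

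The endpoints make this relevant. Section 7.4.1 calls saccadic peak velocity one of the most sensitive measures of sedation. Sections 7.4.3 and 7.4.4 describe adaptive tracking and body sway as responsive to psychoactive agents and sleep deprivation. Section 1.4.4 justifies the crossover by limited variability within patients. Visit-to-visit differences in caffeine work against that premise.

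**Working it through.** No sample-size or power figure is at issue, so the check compares the rules with the visit schedule and adds simple arithmetic.

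**Inputs.** Two periods with two clinic days each (section 3.1). Batteries at -1, 1, 3 and 5 h and the dose at 0 h (Table 2). A cap of 800 mg per day, 100 mg per coffee and about 40 mg per tea (section 4.5).

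**Step 1: days covered by abstinence.** Clinic days = 2 × 2 = 4. Taking the start of the study as period 1 Day 1, the 24-hour rule covers the run-up to 1 day and leaves 4 − 1 = 3 without it.

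| Clinic day | 24 h abstinence before visit | In-unit caffeine rule |
|---|---|---|
| Period 1 Day 1 | yes | daily cap only |
| Period 1 Day 22 | no | daily cap only |
| Period 2 Day 1 | no | daily cap only |
| Period 2 Day 22 | no | daily cap only |

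The pre-dose battery at -1 h is therefore unprotected on three of four days.

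**Step 2: post-dose batteries.** 3 post-dose batteries × 4 days = 12 per patient. The abstinence rule ends at the start of the study and so reaches none of them. Section 1.4.1 puts about 5 hours of break time into each study day and states no caffeine rule for it.

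**Step 3: what the cap allows.** 800 / 100 = 8 cups of coffee, or 800 / 40 = 20 cups of tea, per day. This is a limit, but it does little to standardise test conditions.

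**Step 4: caffeine from the vehicle.** The volume and type of tea are not stated, so the contribution at 0 h ranges from 0 mg (lemonade, juice or a caffeine-free tea) to about 40 mg (a full cup of caffeinated tea). Per kilogram, a full cup is 40 / 25 = 1.6 mg/kg at 25 kg and 40 / 70 = 0.57 mg/kg at 70 kg. Both weights are assumptions. Part B enrols from age 6 with no upper limit in section 4.2.

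**Step 5: the generous reading.** Suppose the start of the study means the start of each study day. The three missing pre-visit windows then close. The 12 post-dose batteries and the tea vehicle remain uncovered. The generous reading also sits badly with the text, since the sentence just before it speaks of the first study day and the alcohol sentence speaks of each visit.

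**The case against.** The strongest reply is that this is a small matter of wording. Several parts of it stand.

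- **Caffeine is not unrestricted.** A reader might infer that it is on three of the four days. The open-ended daily cap rules that out, loose as it is.
- **No reason is given for the caffeine rule.** A reader might infer that the protocol restricts caffeine because it alters the measurements. Section 4.5 says that only of illicit drugs. The relevance of caffeine here is drawn from the nature of the tests.
- **A dose in tea does not breach the abstinence rule.** That rule has already ended by 0 h. The two sections are poorly matched rather than in strict contradiction.
- **A full cup cannot be presumed.** At the stated starting dose, a 25 kg child would need 0.005 × 25 = 0.125 mg, which is 0.125 / 2.5 = 0.05 ml of solution. Nothing in that volume implies a whole cup.
- **Bias between treatments is not shown.** A reader might infer that families would use tea or cola to offset drowsiness on active drug and so mask sedation. The document offers no evidence for this. Both arms have the same vehicle options, the trial is double-blind, and dosing in the clinic is supervised. Any such behaviour could not affect the period 1 Day 1 pre-dose state, and period 2 Day 1 follows a washout of about three weeks. By Day 22 the protocol expects tolerance to sedation (section 1.4.7).
- **Baseline adjustment may help.** The mixed model in section 9.9.2 uses the baseline as a covariate, which may absorb some pre-visit variation. It cannot absorb caffeine taken after the baseline battery.

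The study is also exploratory with no primary endpoint (section 1.4.8), and instructions to parents, which are not visible here, may go further than section 4.5. None of this closes the gap in the stated rule.

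**Conclusion.** The point holds as a cheap improvement. Followed literally, section 4.5 leaves three of four NeuroCart days without pre-visit caffeine abstinence, and all 12 post-dose batteries without any caffeine rule other than a cap of 800 mg per day. The tea option in section 5.1 widens the gap by up to about 40 mg per clinic-day dose, if a full cup of caffeinated tea is used.

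The expected consequence is extra within-patient noise, not a demonstrated bias. Its size cannot be computed, because the document gives no effect of caffeine on any NeuroCart test. The conclusion rests on reading the start of the study as the first study day. On the alternative reading, the in-unit hours and the tea vehicle are still uncovered.

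**What to change.** In section 4.5, word the caffeine abstinence like the alcohol rule: 24 hours before each scheduled visit and throughout the stay in the study unit, until the last battery is complete. Reconcile section 5.1 and the synopsis with section 4.5 on the use of tea for clinic-day doses; the choice of vehicle is the sponsor's. Require that each patient receives the same vehicle on all four study days, and record the vehicle and any caffeine intake on those days.

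The cost is a few wording changes and a line in the instructions to parents. The downside is slightly less choice of drink for the patient.

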## 4.5.1 Contraception requirements

All women of child bearing potential during part A of the study must practice effective contraception during the study and be willing and able to continue contraception for at least 90 days after their last dose of study treatment. Women of child bearing potential are defined as all women physiologically capable of becoming pregnant, unless they meet one of the following conditions:

- Postmenopausal: 12 months of natural (spontaneous) amenorrhea or 6 weeks after surgical bilateral oophorectomy with or without hysterectomy;
- Posthysterectomy.

For the purposes of the study, effective contraception is defined as follows:

 Females: Using 1 or more of the following acceptable methods of contraception: surgical sterilization (e.g., bilateral tubal ligation), intrauterine contraception/device, hormonal contraception, or any 2 barrier methods (a combination of male or female condom with diaphragm, sponge or cervical cap). Abstinence can be considered an acceptable method of contraception at the discretion of the investigator. Periodic abstinence (e.g., calendar, ovulation, symptothermal, post ovulation methods) and withdrawal are not considered acceptable methods of contraception.

## 4.6 Study drug discontinuation and withdrawal

## 4.6.1 Study drug interruption or discontinuation

Before trial medication is administered, changes in the subject health status will be checked. The investigator must temporally interrupt or permanently discontinue the study drug if continued administration of the study drug is believed to be contrary to the best interests of the subject. The interruption or premature discontinuation of study drug might be triggered by an Adverse Event (AE), a diagnostic or therapeutic procedure, an abnormal assessment (e.g., ECG or laboratory abnormalities), or for administrative reasons in particular withdrawal of the subject's consent. The reason for study drug interruption or premature discontinuation must be documented.

## 4.6.2 Subject withdrawal

Subjects have the right to withdraw from the study at any time for any reason. Should a subject decide to withdraw from the study, all efforts should be made to complete and report the observations, particularly the follow-up examinations, as thoroughly as possible. When subjects show signs of resistance or show signs of not wanting to participate during the study, study assessments will be stopped. Signs of resistance include the expression of fear, sadness or anxiety, and will be evaluated in close collaboration with the parents.

## 4.6.3 Replacement policy

Subjects can be replaced if they withdraw from the study on day 1. At most, 2 subjects will be replaced.

## 5 INVESTIGATIONAL DRUG

## 5.1 Investigational drug and matching placebo

## Part A:

- Clonazepam (Rivotril) droplets for oral use, solution 2.5 mg/ml, dissolved in lemonade. Dose: 0.5 mg or 1 mg, both administered to 50% of subjects.

## Part B:

The following substances will be administered:

- Active medication. Clonazepam (Rivotril) droplets for oral use, solution 2.5 mg/ml, dissolved in lemonade, tea or juice.
- Placebo: dissolved in lemonade, tea or juice

Study drug or placebo during part B will be administered to the subjects as follows:

- Day 1-3: Starting dose is 0.005 mg/kg, twice daily (max 0.5 mg, twice daily)
- Day 4-6: 0.01 mg/kg, twice daily (max 0.5 mg, twice daily)
- Day 7-22: 0.015 mg/kg, twice daily (max 0.5 mg, twice daily)

Patients will receive a single starting dose at their first visit of 0.005 mg/kg (max 0.5 mg). Patients will be monitored for 5 hours for safety, PK, and biomarker effect. If the dose on day 1 is well tolerated, patients will take the same dose before bedtime, and continue this regimen as described.

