## Part B

- Active medication. Clonazepam (Rivotril) droplets for oral use, solution 2.5 mg/ml, dissolved in lemonade, tea or juice.
- Placebo: dissolved in lemonade, tea or juice

Study drug or placebo during part B will be administered to the subjects as follows:

- Day 1-3: Starting dose is 0.005 mg/kg, twice daily (max 0.5 mg, twice daily)
- Day 4-6: 0.01 mg/kg, twice daily (max 0.5 mg, twice daily)
- Day 7-22: 0.015 mg/kg, twice daily (max 0.5 mg, twice daily)

Patients will receive a single starting dose at their first visit of 0.005 mg/kg (max 0.5 mg). Patients will be monitored for 5 hours for safety, PK, and biomarker effect. If the dose on day 1 is well tolerated, patients will take the same dose before bedtime, and continue this regimen as described.

After three days, the (adverse) effects will be evaluated by phone. If the dose on day 1 is well tolerated, the dose will be increased to 0.01 mg/kg/day. After another three days, the effects will be evaluated again, after which the dose will be increased to 0.015 mg/kg/day. During these dosing adjustments, the maximum dose will not exceed 0.5 mg, twice daily. In case of relevant adverse events during any of the dose evaluations, the daily dose will be halved. Then, after three days without relevant adverse events, the dose will be increased to the dose that was prescribed at the time adverse events appeared. When relevant adverse events re-appear, subjects will continue at the lowest tolerable dose.

At the end of the study period, clonazepam will be tapered by decreasing the daily dose by 0.01 mg/kg/day every three days.

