# 1.4.6 Safety margin calculations, dose selection, dose escalation, and stopping criteria

The optimal dose of clonazepam to restore the excitation/inhibition imbalance is not known. The dose used pre-clinically (0.0625 mg/kg) [11] is comparable to the doses used in mouse seizures models (0.08-0.5 mg/kg). The HED is 0.0625 mg/kg \* scaling factor 0.08 = 0.005 mg/kg, thus 0.35 mg for an adult male, in the same order as the regular starting dose (0.5 mg twice daily), but much lower than the regular maintenance dose (4-8 mg/day). Although generally considered safe, paradoxical reactions have been described in children and elderly. Usually these occur at higher doses. Other reported side effects include dizziness and drowsiness, which are also dose-related. Tolerance usually develops in 1-2 weeks [22, 23].

The dose used in this study is based on the following rationale:

- 1. The pre-clinically effective dose is similar to the starting dose in preclinical seizure models, and the human equivalent dose is in the range of the recommended starting dose for seizures in humans.
- 2. The dose is identical to the dose given to the case of the 12 year old ARID1B patient currently on clonazepam with good clinical effect and absence of toxicity.
- 3. Clonazepam is a registered drug. The recommended starting dose is the same as given in this study.

Therefore, the patients will receive a single starting dose at their first visit of 0.005 mg/kg (max 0.5 mg). Patients will be monitored for 5 hours for safety, PK, and biomarker effect. If the dose on day 1 is well tolerated, patients will take the same dose before bedtime, and continue this regimen as described.

After three days, the (adverse) effects will be evaluated by phone. If the dose on day 1 is well tolerated, the dose will be increased to 0.01 mg/kg/day. After another three days, the effects will be evaluated again, after which the dose will be increased to 0.015 mg/kg/day. During these dosing adjustments, the maximum dose will not exceed 0.5 mg, twice daily. In case of relevant adverse events during any of the dose evaluations, the daily dose will be halved. Then, after three days without relevant adverse events, the dose will be increased to the dose that was prescribed at the time adverse events appeared. When relevant adverse events re-appear, subjects will continue at the lowest tolerable dose.

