## 5.2 Study drug up- and down-titration

After three days, the (adverse) effects will be evaluated by phone. In the absence of adverse events, dose will be increased to 0.01 mg/kg/day. After another three days, the effects will be evaluated again, after which the dose will be increased to 0.015 mg/kg/day. During these dosing adjustments, the maximum dose will not be allowed to exceed 0.5 mg twice daily. In case of reported adverse events during any of the dose evaluations, the daily dose will be halved. Then, after three days without adverse events, the dose will be increased to the dose that was prescribed at the time adverse events appeared. When adverse events re-appear, subjects will continue at the lowest tolerable dose.

At the end of the study period, starting in the evening of Day 22, clonazepam will be tapered by decreasing the daily dose by 0.01 mg/kg/day every three days.

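### Part B gives two incompatible dose titrations: 0.005, 0.01 and 0.015 mg/kg twice daily in the schedule, but 0.01 then 0.015 mg/kg per day in the escalation rules

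*Protocol*

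**What the plan says.** **Schedule.** The dosing list in section 5.1, Part B, and the same list in the synopsis start at 0.005 mg/kg twice daily on Days 1-3. They continue with "Day 4-6: 0.01 mg/kg, twice daily (max 0.5 mg, twice daily") and "Day 7-22: 0.015 mg/kg, twice daily (max 0.5 mg, twice daily"). Both places add that the Day 1 clinic dose, if tolerated, is taken again at bedtime, so 0.005 mg/kg is a per-administration dose.

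**Escalation rules.** After the first phone evaluation, section 5.2 states: "In the absence of adverse events, dose will be increased to 0.01 mg/kg/day". The synopsis has: "If the dose on day 1 is well tolerated, the dose will be increased to 0.01 mg/kg/day", and section 1.4.6 has the same rule. For the second step, section 1.4.6 says "after which the dose will be increased to 0.015 mg/kg/day", and section 5.2 and the synopsis agree. The synopsis therefore carries both versions. All these places cap the dose at 0.5 mg twice daily.

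**Taper.** Section 5.2 says "clonazepam will be tapered by decreasing the daily dose by 0.01 mg/kg/day every three days", while section 3.1 describes each period as 22 days "plus a down titration period of ±3 days".

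**Trigger for changing the dose.** Section 5.2 requires that no adverse event has occurred and halves the dose for any reported event. The synopsis and section 1.4.6 ask for good tolerability and halve only for relevant events.

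**The concern.** The same numbers, 0.01 and 0.015, appear once per administration and once per day, which is a factor of two. These are operative dosing rules for children from 6 years (section 4.2) and for incapacitated adults, and between Day 1 and Day 22 the drug is given at home. The amendment log shows that the regimen of the first six days and its escalation decision were already changed once for safety; this is context only.

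The risk runs both ways. If the per-day rule is intended, following the schedule doubles the dose from Day 4 in children up to about 33 kg. If the twice-daily schedule is intended, following section 5.2 gives no first increase and half the maintenance dose in those children. The Day 22 NeuroCart tests, ABC and CGI-I would then reflect a lower dose than planned. If different staff follow different sections, the maintenance dose would also vary between patients for no planned reason.

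**Working it through.** **Inputs**

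- Schedule (5.1, synopsis): 0.005, 0.010 and 0.015 mg/kg per administration, two administrations a day.
- Escalation rules (5.2, 1.4.6, synopsis): 0.010, then 0.015 mg/kg per day.
- Cap: 0.5 mg twice daily = 1.0 mg/day.
- Taper: steps of 0.01 mg/kg per day every three days (5.2).
- Adult reference weight: section 1.4.6 converts 0.005 mg/kg as "thus 0.35 mg for an adult male", so 0.35 / 0.005 = 70 kg.

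**Step 1: can the escalation figures be reproduced from the schedule?** No.

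- Days 1-3: 2 × 0.005 = 0.010 mg/kg/day.
- Days 4-6: 2 × 0.010 = 0.020 mg/kg/day; the rules say 0.010, so the first increase is from 0.010 to 0.010.
- Days 7-22: 2 × 0.015 = 0.030 mg/kg/day; the rules say 0.015.

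Before the cap, rules / schedule = 0.010 / 0.020 = 0.015 / 0.030 = 0.50 on Days 4-22.

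**Step 2: dose in mg.** Daily dose = min(rate × weight, 1.0 mg). Entries are schedule against escalation rules, in mg/day.

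| Weight | Days 4-6 | Ratio | Days 7-22 | Ratio |
|---|---|---|---|---|
| 20 kg | 0.40 vs 0.20 | 2.0 | 0.60 vs 0.30 | 2.0 |
| 33.3 kg | 0.67 vs 0.33 | 2.0 | 1.0 vs 0.50 | 2.0 |
| 40 kg | 0.80 vs 0.40 | 2.0 | 1.0 vs 0.60 | 1.67 |
| 50 kg | 1.0 vs 0.50 | 2.0 | 1.0 vs 0.75 | 1.33 |
| 60 kg | 1.0 vs 0.60 | 1.67 | 1.0 vs 0.90 | 1.11 |
| 70 kg | 1.0 vs 0.70 | 1.43 | 1.0 vs 1.0 | 1.0 |
| 100 kg | 1.0 vs 1.0 | 1.0 | 1.0 vs 1.0 | 1.0 |

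On Days 4-6 the cap binds from 1.0 / 0.020 = 50 kg under the schedule and from 1.0 / 0.010 = 100 kg under the rules. On Days 7-22 it binds from 1.0 / 0.030 = 33.3 kg and from 1.0 / 0.015 = 66.7 kg. Days 1-3 do not differ at any weight.

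**Step 3: does the taper show which version is meant?** Count days of reduced dosing, taking the last step to zero.

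- Schedule, uncapped: 0.030 → 0.020 (3 days) → 0.010 (3 days) → 0, so 6 days.
- Schedule, 40 kg, capped at 1.0 / 40 = 0.025: → 0.015 (3 days) → 0.005 (3 days) → 0, so 6 days.
- Schedule, 50 kg, capped at 1.0 / 50 = 0.020: → 0.010 (3 days) → 0, so 3 days.
- Escalation rules: 0.015 → 0.005 (3 days) → 0, so 3 days.

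The down-titration of about 3 days in section 3.1 fits the per-day rules at any weight under 100 kg. It fits the schedule only from 50 kg to under 100 kg; below 50 kg the schedule needs 6 days.

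**Step 4: evidence for each reading**

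- For twice daily: an increase needs a step, and the per-day rules have none on Day 4; the cap is stated twice daily; one taper step of 0.01 mg/kg per day equals one twice-daily titration step (2 × 0.005).
- For per day: the wording appears in three places, and the taper length in section 3.1 fits it under 50 kg.

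**The case against.** The strongest reply is that this is a unit slip copied between paragraphs and that the protocol as a whole points to twice daily. The numbers and three-day steps match the schedule, the word for an increase has no meaning at the first step if read per day, and the Day 3 phone evaluation would have no increase to decide. The schedule is also the explicit administration list, and the taper length in section 3.1 is approximate and separates the readings only under 50 kg. This has weight: twice daily is arguably the more natural reading. But no text seen says which version governs, and section 5.2 is where a physician would look when making the Day 3 and Day 6 decisions. A dose for children should not rest on inference.

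One limit stands. The text of section 1.3, on clinical information about the drug, was not available here. Section 1.4.6 equates the study dose with that of a 12-year-old patient already treated, but the text seen does not give that patient's dose.

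The consequences are also bounded. Both versions stop at 0.5 mg twice daily, which section 1.4.6 calls the regular starting dose, far below the regular 4-8 mg/day maintenance (no separate paediatric range is given). Phone evaluations, dose halving and investigator stopping apply either way, and the first five patients are aged 12 or over (section 1.4.3). These points limit the harm but do not remove the contradiction. Medication diaries (9.7.3) and Day 22 saliva samples (Table 2) would help show what was taken, but only afterwards.

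**Conclusion.** The concern holds and must be fixed. The current text contains two titrations that differ by a factor of two in mg/kg on Days 4-22, and the first step of one of them is no increase at all. In mg, the maintenance difference is two-fold up to about 33 kg, 1.67-fold at 40 kg and 1.33-fold at 50 kg, and nil from about 67 kg. On Days 4-6 it is two-fold up to 50 kg and nil from 100 kg. At the 70 kg adult weight only Days 4-6 differ (1.43-fold).

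Days 1-3 and the Day 1 acute tests do not depend on the answer, and the within-patient placebo comparison stays valid at whatever dose was given. What is uncertain is the dose to which the Day 22 results refer, and the safety of lighter patients.

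Weights other than 70 kg are illustrative. The protocol gives no weight distribution, so the number of patients affected is unknown. The taper counts assume that a patient at 0.01 mg/kg per day or less stops at the next step. The rating rests on the dose conflict alone, not on the taper length or the adverse-event trigger.

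**What to change.** The clinical team confirms the intended regimen, and one version is used throughout. The cap of 0.5 mg twice daily stays in either case.

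- **If twice daily:** in the synopsis, 1.4.6 and 5.2, change the escalation targets to 0.01 mg/kg twice daily and then 0.015 mg/kg twice daily (0.02 and 0.03 mg/kg per day).
- **If per day:** in the synopsis and 5.1, change the schedule to 0.005 mg/kg twice daily on Days 1-6 and 0.015 / 2 = 0.0075 mg/kg twice daily on Days 7-22, or state the first step that was meant.
- **Either way:** in 3.1, replace the fixed 3-day down-titration, for both periods, with wording that runs until the taper in 5.2 is complete.
- **Secondary:** decide whether any adverse event or only a clinically relevant one blocks escalation and halves the dose, and use that wording in the synopsis, 1.4.1, 1.4.6 and 5.2.

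The cost is wording in a few sections, in one substantial amendment, plus a check of pharmacy labels, dosing sheets and the consent document, with updates where needed. The earlier dosing change also altered the consent document. Patient numbers, visits and analysis do not change.
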